1.4 Handling of Missing Date

For any partially or completely missing date of testing, the scheduled testing day (Day 1, 3, 5, 7) will be used for days to test positivity.

1.5 Primary Analysis

- Objective: The proportion of students/staff with positive COVID-19 test following known within-school exposure and the proportion of exposures undergoing the test-to-stay protocol that result in additional transmission will be summarized overall, by student or staff, by school district, by school level.
 - To account for the within-school correlation of outcomes, 95% CI will be estimated for the proportion using a generalized estimating equations approach using a working independence correlation structure (Zeger et al. 1988).
 - Objective: Days to test positivity among those exposed to SARS-CoV-2 and undergoing the test-to-stay protocol will be summarized by median and interquartile ranges and nonparametric estimate of test positivity probability will be plotted.

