Yet, current policies and procedures requiring quarantine after close contact exposures to limit further spread have led to hundreds of thousands of missed school days and have threatened the school workforce, greatly impeding school operations and the ability of children to appropriately learn. In the fourth quarter of 2021 in NC alone, more than 40,000 students and staff were required to quarantine as a result of being a close contact of a COVID-19 case (unpublished). Fortunately, recent CDC and local guidance have eliminated quarantines for most exposed, unvaccinated, asymptomatic children who are wearing a mask and who are in close contact with another masked, infected child within the classroom setting. However, many quarantines continue to result in unvaccinated adults, children exposed to infected adults, and masked exposures occurring outside of the classroom (e.g., athletics or busing). Moreover, schools and local governments are steadily lifting mask mandates, even as local community cases rise, contributing to exponential increases in quarantines that not only keep children and staff out of schools and parents out of work, but have often overwhelmed school resources and the public health system.

To address the issue of quarantines while ensuring that the school and surrounding community remain safe from SARS-CoV-2 spread, some locales have begun implementing a "test to stay strategy", whereby a close contact undergoes serial testing over a specified duration of time.

The close contact must wear a mask during this time period but is not required to undergo quarantine as long as the screening tests remain negative and the contact remains asymptomatic. While this strategy is supported by strong scientific premise and initial data are promising, the impact of this strategy on quarantine, and secondary and tertiary within-school transmission has not been systematically evaluated.

This study will partner with schools to allow students and staff to remain in school following exposure if they continue to test negative for COVID-19 over pre-determined intervals. This study aims to collect data to assess the spread of SARS-CoV-2 in school communities with varying mitigation strategies to provide data-backed guidelines for mitigation strategies in schools. The study team will work with NCDHHS and a safety monitoring team on a weekly basis to interpret data, evaluate safety, and design next steps (e.g. testing frequency and timing).

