8.2.1 Primary Analysis

For the primary endpoint the proportion of students/staff with positive COVID-19 test will be reported and the trend by week will be presented in graphical form. To account for the within-school correlation of outcomes, 95% confidence intervals will be estimated for the proportion using a generalized estimating equations approach using a working independence correlation structure.¹²

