8.3 Sample Size Considerations

No formal sample size calculation was completed for this study. This study will enroll up to 1,000,000 participants.

9 Future Use of Study Records

The research data collected in this study, and provided to the sponsor, will be kept indefinitely.

Information about this study, including study results, will be published without further permission from the participant as detailed in the informed consent form. Participants will not be identified in any publications or presentations made about the study.

After the study is completed, information about the study, including study data, may be provided to the National Institutes of Health (NIH). Identifiable data will be kept at the DCRI and the DCRI will not share these data with the NIH. With NIH approval, the data submitted may be used by other researchers for future research. The study data submitted will be de-identified, meaning it will not include any information that can identify the participant. The study team may also share the de-identified study data with other researchers. When the participant's de-identified study data are provided to other researchers for the purposes of future research, it will be done without obtaining additional permission.

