1.6 Secondary Analysis

- Objective: The proportion of students/staff who reported masking and unmasking will be summarized and presented in a bar chart to see the trend by testing day.
 - The primary analysis will be repeated for masked and unmasked participants (students and staff) separately.
 - The primary analysis will be repeated for masked and unmasked source of exposure separately.
- Objective: School absences will be analyzed by absences due to symptoms, positive COVID-19 test, or due to quarantine for exposure to SARS-CoV-2.
 - To account for the within-school correlation of outcomes, analyses will be conducted using a generalized estimating equations approach using a loglink suitable for count outcomes, with a working independence correlation structure (Zeger et al. 1988).

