2.7 Secondary Analysis

- Objective: The primary analysis will be repeated for during the period when the omicron variant comprised most COVID-19 cases (1/3/2022–1/28/2022)

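### Manuscript 1's masked and unmasked proportions are open to confounding by calendar time: no exposure window, weekly trend or period control is planned

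*SAP*

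**What the plan says.** Protocol 8.2.1 plans the proportion of students and staff testing positive and adds that "the trend by week will be presented in graphical form". Protocol 8.2.2 adds a risk difference for each semester as well as overall.

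SAP 1.5, the Manuscript 1 counterpart, says the proportions "will be summarized overall, by student or staff, by school district, by school level". It has no week, semester or other calendar breakdown. The one trend in Manuscript 1 is in SAP 1.6, where the proportion reporting masking is "presented in a bar chart to see the trend by testing day". That axis is time since exposure, not calendar time.

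On masking, SAP 1.6 says: "The primary analysis will be repeated for masked and unmasked participants (students and staff) separately", and likewise "The primary analysis will be repeated for masked and unmasked source of exposure separately". Neither line names a covariate or a period term. The matching aim in SAP 1.1 is worded as an effect of individual mitigation measures such as masks.

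SAP 1.2 takes every enrolled participant with a within-school exposure and gives no exposure dates. Manuscripts 2 and 3 each state theirs: 29 November 2021 to 28 January 2022 (SAP 2.2) and 8 January to 15 February 2022 (SAP 3.3). SAP 2.7 repeats the Manuscript 2 analysis for "the period when the omicron variant comprised most COVID-19 cases", given as 3 to 28 January 2022.

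**The concern.** Calendar time confounds a masked-versus-unmasked comparison when the mix of masked exposures and the background risk both change over time. The documents give reason to expect each. On risk, the SAP sets omicron apart as a period worth its own analysis. On masking, Protocol 1.1.1 says that "schools and local governments are steadily lifting mask mandates, even as local community cases rise". A third factor may also move: Protocol 3.1 and 5.4 allow the number and timing of tests to change after the initial phase, which could alter how many infections are found.

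Secondary objective 1 is at stake. Readers will set the masked and unmasked proportions side by side, and a difference produced by when the exposures happened would look like a difference produced by masks. The overall primary proportion is also an average over periods, weighted by enrollment, and the weekly plot that would have shown this is no longer planned.

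**Working it through.** **Does Manuscript 1 span the omicron start?** SAP 1.2 sets no date limit. The original protocol is dated 17 September 2021 and the Manuscript 1 plan 27 June 2022. Protocol section 10 (version of 30 November 2021) says schools were already sending data. Manuscript 2's window includes within-school exposures on both sides of 3 January 2022. Read as written, Manuscript 1 pools both sides. This is a strong inference, not a stated fact.

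**Is there any control for period?** The generalized estimating equations in SAP 1.5 address within-school correlation, not confounding. District summaries do not separate periods within a district. SAP 1.7 only allows unspecified exploratory subgroups.

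**How large could the effect be?** There is no planned figure to reproduce: Protocol 8.3 says "No formal sample size calculation was completed for this study", and neither document gives mask use or positivity by date. All inputs below are assumptions.

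- Two periods, holding shares w1 and w2 = 1 − w1 of exposures; w1 = 0.3, 0.5 or 0.7.
- Risk p1 = 2% in period 1; p2 = 2%, 4% or 8% in period 2. Risk is the same for masked and unmasked, so the true risk ratio (RR) is 1.00.
- Masked shares m1 and m2: 90% then 90%, 90% then 70%, 90% then 50%, or 70% then 90%.

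Pooled masked risk M = (w1·m1·p1 + w2·m2·p2) / (w1·m1 + w2·m2). Pooled unmasked risk U is the same with 1 − m in place of m. Pooled RR = M/U.

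Examples with w1 = 0.5:

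- *Masking 90% then 50%, risk 2% then 8%.* M = (0.009 + 0.020)/0.70 = 4.1%; U = (0.001 + 0.020)/0.30 = 7.0%; RR = 0.59.
- *Masking 90% then 70%, risk 2% then 4%.* M = (0.009 + 0.014)/0.80 = 2.9%; U = (0.001 + 0.006)/0.20 = 3.5%; RR = 0.82.
- *Masking 70% then 90%, risk 2% then 8%.* M = (0.007 + 0.036)/0.80 = 5.4%; U = (0.003 + 0.004)/0.20 = 3.5%; RR = 1.54.
- *Masking 90% in both, risk 2% then 8%.* M = U = 5.0%; RR = 1.00.

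Pooled RR over the three values of w1:

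| Masking | Risk 2% then 4% | Risk 2% then 8% |
|---|---|---|
| 90% then 70% | 0.80 to 0.88 | 0.65 to 0.81 |
| 90% then 50% | 0.71 to 0.81 | 0.52 to 0.72 |
| 70% then 90% | 1.20 to 1.25 | 1.41 to 1.54 |
| 90% then 90% | 1.00 | 1.00 |

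With risk constant at 2%, RR is 1.00 in every row. Within each period the two groups have the same risk, so the period-stratified RR is 1.00 in every scenario by construction.

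**Could it look like a finding?** Assume 2,000 exposures and ignore clustering. The first example (1,400 masked, 600 unmasked) gives a difference of 7.0% − 4.1% = 2.9 percentage points, which would reach two-sided 5% about 75% of the time. The second (1,600 masked, 400 unmasked) would do so about 11% of the time.

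**The case against.** A reader might infer that the comparison *is* confounded, and in favour of masks. The documents do not show that. They give neither mask use nor positivity by date. The sentence on lifted mandates is undated background in a protocol version of 30 November 2021, before the SAP's omicron start. Optionally masked districts supply Manuscript 2 data from 29 November 2021, and the Manuscript 3 sites had universal masking for exposures from 8 January to 15 February 2022. Unmasked exposures before omicron and masked exposures during it are both plausible, so the bias could run either way or be nil. This objection stands and limits the conclusion.

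A reader might also infer that losing the weekly plot causes the confounding. It does not. The plot is descriptive and adjusts nothing, and the unadjusted mask strata come from Protocol 8.2.2 itself. The omitted trend and the missing control are separate gaps. Nor is the by-semester risk difference clearly a mask contrast; Protocol 8.2.2 describes it as between schools.

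Finally, SAP 1.6 specifies separate strata and no masked-versus-unmasked ratio, difference or test. That is a fair defence if the strata are presented as description. It is weaker against an aim worded as an effect.

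**Conclusion.** The point holds as a gap in planning, not as a demonstrated bias. The text establishes that Manuscript 1 states no exposure window, omits both calendar-time analyses in the protocol, and repeats its analysis by masking with no period control, while the same SAP isolates an omicron period elsewhere. The masked and unmasked proportions are therefore open to confounding by calendar time.

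The possible size rests wholly on the assumed inputs: a spurious ratio of about 0.5 to 0.9 or 1.2 to 1.5, according to direction, and 1.0 if masking or risk is stable. The significance figures also depend on an assumed 2,000 exposures and no clustering. The change is worth making because a stated objective depends on this comparison and the remedy is inexpensive.

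**What to change.** In SAP 1.5:

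- State the Manuscript 1 exposure window.
- Restore the weekly plot of positivity for students and staff from Protocol 8.2.1.

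In SAP 1.6:

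- Show the participant-masking and source-masking analyses by calendar period. Use either semester, the division already in Protocol 8.2.2, or before, during and after 3 to 28 January 2022. The third category is needed because the SAP's omicron period is closed at 28 January, the end of Manuscript 2's data, and later dates are not classified.
- Base any statement about a mask effect on the period-stratified estimate, or on a generalized estimating equations model with a period term. Label the pooled strata descriptive.

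The cost is SAP wording and some table rows; Protocol 5.3 already collects when the exposure occurred. Precision within each period will be lower, and some cells may be sparse. Stratifying by period deals only with calendar time, so differences between masked and unmasked exposures in setting, vaccination or district would remain.

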8.2.2 Secondary Analysis

The proportion and number of students/staff who reported masking and unmasking will be reported and presented in graphical form. The primary analysis will be repeated for masked and unmasked participants (students and staff) separately. The primary analysis will be repeated for masked and unmasked source of exposure separately.

School absences will be analyzed by absences due to symptoms, positive COVID-19 test, or due to quarantine for exposure to SARS-CoV-2. To account for the within-school correlation of outcomes, analyses will be conducted using a generalized estimating equations approach using a loglink suitable for count outcomes, with a working independence correlation structure.

To account for within-school correlation, a risk between the schools using a generalized estimating equation approach with an identity link and a working independence correlation structure will be estimated. The risk difference will be estimated for each semester during the study period, as well as overall. Students will be censored by end of data or study withdrawal. Censoring will be addressed by incorporating inverse-probability censoring weights into the regression model, with censoring risk estimated with a Kaplan-Meier estimator.

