3.2 Data

TTS data collected from K-12 students and staff with household exposures within 4 districts and 1 charter school in North Carolina (NC) employing universal masking.

- Establish population cutoff
 - [name] (Statistical programmer): Here are the number of household exposures with test results on or after days 5, 7, and 9: \geq Day 5 = 282; \geq Day 7 = 251; \geq Day 9 = 214
 - [name] (Project leader): Given that ~65% of population made it into analysis eligible population for day 9, we will use this day as the cutoff, which is consistent with CDC guidance for household close contacts

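### The school-clustered GEE interval in SAP 1.5 has zero width in any row with one contributing school and is too narrow in rows with few schools, and the SAP gives no safeguard

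*SAP*

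**What the plan says.** SAP 1.5 (Manuscript #1) covers two sets of primary proportions: positive tests among exposed students and staff, and exposures that lead to additional transmission. It says they "will be summarized overall, by student or staff, by school district, by school level". The bullet beneath gives the interval: "To account for the within-school correlation of outcomes", the "95% CI will be estimated for the proportion using a generalized estimating equations approach using a working independence correlation structure". Protocol 8.2.1 names the same method ("95% confidence intervals will be estimated for the proportion using a generalized estimating equations approach using a working independence correlation structure") but has no split by district.

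Neither text states a small-sample correction, a t reference, a minimum number of schools, or a fallback for rows with one school or no events. SAP 1.6 repeats the primary analysis by participant masking and by masking of the source, which makes the rows thinner. Protocol 8.3 says "No formal sample size calculation was completed for this study". The number of schools per district appears nowhere. A sparse-data fallback (Clopper-Pearson) appears only in SAP 3.7, for Manuscript #3.

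**The concern.** With working independence, the model-based standard error treats everyone in a school as independent, so it cannot do what the bullet says it is for. The robust (sandwich) variance must therefore be meant, although the SAP does not use the word. That variance is estimated from the spread of school-level residual totals. It needs many schools to work well, and it cannot be estimated from one. A breakdown by district or school level, repeated by masking status, is where few schools per row are most likely.

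At stake are the intervals on primary endpoints. A district row could be printed with no uncertainty at all, or with much less than it has. A reader comparing rows could then take chance variation for a real difference in transmission between districts, in a study meant to inform quarantine policy.

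**Working it through.** **Inputs from the documents.** The cluster is the school. The method is GEE with working independence, and the nominal level is 95% (SAP 1.5). This is the only figure the plan states on the point. It cannot be reproduced for the actual rows, because the number of schools per row is not given.

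**Inputs assumed, not in the documents.** Positivity 2-10%, ICC 0.02-0.05, 30-100 exposures per school, unequal school sizes. The counts 6/120 and 0/120 are illustrations.

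**Step 1: the variance.** Let school k have x_k positives among m_k exposed, with N = Σ m_k and p = Σ x_k / N. For an intercept-only model with working independence, on the identity scale,

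Var(p) = Σ_k (x_k − m_k p)² / N².

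On the logit scale this is divided by [p(1 − p)]².

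**Step 2: one school.** Here p = x_1/m_1, so x_1 − m_1 p = 0 and the variance is exactly zero. This is algebra and needs no assumption. For 6/120: p = 0.05, the residual total is 6 − 120 × 0.05 = 0, and the interval is 5.0% to 5.0%. A GEE fit returned a standard error of 5.6e-17 (logit) and 3.3e-17 (identity), which is zero to machine precision. The Clopper-Pearson interval for 6/120 is 1.9% to 10.6%. A joint model with district indicators also gives zero for a one-school district.

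**Step 3: no positives.** Every x_k and p are zero, so every residual total is zero. The identity-scale interval is 0% to 0%, and the logit estimate is not finite. The exact upper limit for 0/120 would be 1 − 0.025^(1/120) = 3.0%.

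**Step 4: few schools, equal-size approximation.** With K schools of equal size, the uncorrected sandwich is (K − 1)/K times the unbiased variance, and the ratio follows t on K − 1 df. So

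coverage = 2 F_t(K−1)(1.96 √((K − 1)/K)) − 1.

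For K = 2, 1.96 × √0.5 = 1.386 on 1 df gives 60.2%. For K = 5, 1.96 × √0.8 = 1.753 on 4 df gives 84.6%. The other values are 74.9% (K = 3), 90.4% (10), 92.9% (20) and 94.0% (40).

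**Step 5: few schools, simulation.** Beta-binomial outcomes, unequal school sizes, logit link and the assumed ranges above; coverage is among samples where an estimate exists. The last column uses a Mancl-DeRouen sandwich with t on K − 1 df.

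| Schools | As written | Corrected |
|---|---|---|
| 2 | 54-68% | median width about 99-100 points |
| 3 | 69-81% | 95-98% |
| 5 | 77-89% | 95-98% |
| 10 | 83-92% | 92-98% |
| 40 | 91-93% | not needed to make the point |

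The correction restores coverage from three schools up. At two schools the corrected interval spans almost the whole scale, so it tells the reader nothing.

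**The case against.** **No affected row is documented.** This is the strongest objection, and it stands. A reader might infer from SAP 3.2 ("within 4 districts and 1 charter school in North Carolina (NC) employing universal masking") that the charter school will be a zero-width row. That section describes the Manuscript #3 household data, which SAP 3.6 analyses with a district random effect and not with GEE. Manuscript #1 requires exposure in the school setting, and nothing says the charter school contributes a row there. It shows only that a one-school unit can occur.

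**Protocol 8.2.2.** A reader might also infer that the planned risk difference has zero standard error, since the protocol says that "a risk between the schools using a generalized estimating equation approach with an identity link and a working independence correlation structure will be estimated". The sentence names no contrast, and the SAP does not carry it forward. If it means one school against another, each school is fitted exactly (6/120 and 12/100 leave residual totals of 6 − 120 × 0.05 = 0 and 12 − 100 × 0.12 = 0), and the robust standard error would be zero around a 7-point difference. If it means groups of schools, it would not be. The text does not settle this, so the zero-variance claim is not made for 8.2.2.

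**Is every row meant to get this interval?** SAP 1.5 does not say so outright. But the interval bullet sits directly under the breakdown and offers no other method, so that is the fair reading.

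**Size.** The shortfall depends on assumed inputs. In very sparse rows with equal-sized schools (2% positivity, 30 per school, 5 schools), coverage where an estimate exists is about 94%, although 5-16% of such samples have no estimate. The study is descriptive, no test between districts is planned, and a zero-width interval would probably be noticed in the output. The under-coverage at 2 to 5 schools would not be visible.

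**Conclusion.** The point holds for the rows of SAP 1.5, and their repeats in 1.6, that draw on few schools. The zero variance with one school is exact. The under-coverage is large at about 2 to 5 schools, moderate at 10, and about 2 to 4 points at 40 (95 − 93 and 95 − 91), under the assumed positivity, ICC and school sizes. The overall interval is little affected if many schools contribute. How many rows are affected cannot be known from the documents. Following the text as written gives a wrong interval in such rows, so this is more than missing detail.

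**What to change.** In SAP 1.5, and for the repeats in 1.6:

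- State that the interval uses a bias-corrected (Mancl-DeRouen) sandwich on the logit scale, with t on (schools − 1) df, for rows with at least a pre-stated minimum number of schools, for example 3.
- For rows below that minimum or with no positives, give counts and a Clopper-Pearson interval marked as not cluster-adjusted.
- Report the number of contributing schools in every row.

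The cost is a few lines of SAP text and a programming change, with no new data. Some district intervals become wider: at three schools the median corrected width was about 35 points in one assumed scenario (positivity 10%, ICC 0.02, about 60 exposures per school), so the sponsor may prefer a higher minimum. The Clopper-Pearson fallback ignores clustering and does not generalise beyond the schools observed, so the label matters. Separately, if the risk difference in Protocol 8.2.2 is kept, its contrast should be defined; a comparison of single schools cannot use school as the cluster.
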